The QDOT FAST study is a prospective, multi-center, non-randomized clinical study to evaluate the safety and acute performance of the THERMOCOOL SMARTTOUCH® SF-5D system with the nMARQ™ Multi-Channel RF Generator with TGA mode in patients diagnosed with Paroxysmal Atrial Fibrillation (PAF) during standard electrophysiology mapping and RF ablation procedures.

The study population will consist of approximate 50 subjects with PAF as an indication for radiofrequency(RF) ablation. The study will be conducted up to 10 sites in Europe. Follow-up will be conducted at 7 days, 1-month and 3-month post-ablation procedure.

2 Treatment Assignment

All subjects will receive ablation via the THERMOCOOL SMARTTOUCH® SF-5D system and will attempt a very short ablation using the TGA mode (Temperature Guided Ablation).

3 Randomization and Blinding Procedures

Randomizaiton and blinding procedures do not apply for this study.

4 Interval Windows

Refer to protocol Table 3 Summary of Subject Assessment for subject treatments and evaluations.

5 Primary and Secondary Endpoint(s) and Associated Hypotheses

This is a fesibility study and no statistical hypotheses are tested for either primary endpoints or secondary endpoints.

5.1 Primary Endpoint(s) and Associated Hypotheses

Acute Safety

The primary safety endpoint is the incidence of Primary Adverse Events (PAEs) (within seven (7) days of the initial mapping and ablation procedure). PAEs include the following AEs:

Atrio-Esophageal Fistula*	Phrenic Nerve Paralysis
---------------------------	-------------------------

Cardiac Tamponade/perforation	Pulmonary Vein Stenosis*
Death*	Stroke/CVA
Major Vascular Access Complication/Bleeding	Thromboembolism
Myocardial Infarction	TIA

**Device or procedure related death, pulmonary vein stenosis and atrio-esophageal fistula that occur greater than one week (7 days) post-procedure are considered and analyzed as primary AEs.*

Acute Effectiveness

Acute Procedural Success defined as confirmation of entrance block in all targeted PVs after adenosine and/or isoproterenol challenge. The use of a non-study catheter for PVI will be considered an effectiveness failure.

5.2 Secondary Endpoints

- **Safety**
 - Incidence of Serious Adverse Device Effects (SADEs)
 - Incidence of Serious Adverse Events (SAEs) within 7 days (early-onset), >7-30 days (peri-procedural) and >30 days (late onset) of initial ablation procedure
 - Incidence of non-serious adverse events
 - Incidence of pre-and post-ablation asymptomatic and symptomatic cerebral emboli as determined by MRI evaluations
 - Incidence of new or worsening neurological deficits compared to baseline
 - Summary of NIHSS, mRS and MoCA scores at baseline and follow-up timepoints
- **Effectiveness**
 - PVI achieved with TGA mode only among all targeted veins and by subject
 - PVI achieved with combined use of TGA and Q-mode among all targeted veins and by subject
 - Ablation of acute reconnection (touch-up) among all targeted veins and by subject
 - Ablation by a non-study catheter among all targeted veins and by subject
 - Touch-up applications with TGA, Q-mode and non-study catheter applications
- **Additional analyses on procedural data, including but not limited to:**
 - Use of QDOT Micro™ catheter ablation outside the PV area
 - Use of a non-study catheter for ablation outside the PV area

- Total procedure time, mapping time, PV ablation time, total ablation time, RF application time, LA dwell time
- Total number of RF applications, % TGA applications and % Q-mode applications
- Anatomical location of touch-up applications
- Temperature, power, contact force, impedance
- Total Fluoroscopy time/dose

6 Levels of Significance

All data will be summarized by descriptive analyses. No formal statistical inference will be made. Sub-analyses will be done for subjects where TGA was the only application mode used and for subjects where applications were done through a combination of TGA and Q-mode. Where confidence intervals are used they will be two-sided 95% confidence intervals, unless stated otherwise.

7 Analysis Sets

The following analysis populations will be used to complete the analyses of data:

- **Safety Population (SP):** The safety population will include all enrolled subjects who have the investigational device inserted, regardless if RF energy is delivered. All safety analyses will be performed on the Safety Population.
- **Effectiveness Population (EP):** The effectiveness population will include all enrolled subjects, have had the investigational device inserted and underwent ablation with the study catheter used in conjunction with TGA mode for PVI. The subjects without any TGA mode application for PVI will be excluded from the effectiveness population. All effectiveness analysis will be performed on the Effectiveness Population.
- **Neurological Assessment Evaluable (NAE) Population:** The NAE Population will include all enrolled subjects have been treated with the study catheter and have any post-ablation neurological assessment. Assessment of incidence of new lesions requires availability of pre-and post MRI. The subjects without pre-MRI but no lesion on post-MRI will be included in the NAE population. Assessment of incidence of new deficits requires availability of pre-and post-neurological evaluation. Analysis of neurological data will be performed on the NAE Population.

8 Sample Size Justification

This is a clinical feasibility study for evaluation of safety and acute performance of THERMOCOOL SMARTTOUCH® SF-5D system with TGA mode application for PVI. This clinical investigation is intended to provide preliminary estimates of safety and acute performance. Enrollment in the clinical investigation will be approximate 50 subjects,

distributed over up to 10 centers in Europe. Minimum attrition is expected for safety assessment. No more than 10% attrition is expected to assess effectiveness outcomes.

Because this study is a feasibility study, there is no statistical power calculation and no hypothesis to be tested. 50 subjects are deemed sufficient to clinically characterize safety and acute outcomes.

9 Data Monitoring Committee (DMC)

Safety review will be performed by the medical safety officer as described by Safety Management Plan.

10 Analyses to be Conducted

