#### **8.2.3. *Data collection during study ablation procedure***

Procedural data collection will be done through generator files, CARTO® datafiles, procedural worksheets and subject medical files. Documentation of procedural data will be kept in the subject's CRF, back-up generator files and back-up CARTO® data files for study analysis.

At the completion of the study ablation procedure two back-up copies of the CARTO and generator log files will be made. One copy should be kept at the site within the investigator site or patient binders, and one fully anonymized copy will be sent to the sponsor, in a timely manner

The Carto and Generator data (electronic raw data) collected during the Study Ablation procedure will be anonymized (or de-identified) prior to its transfer to the Sponsor. Data will be verified during this lifecycle (Data Transfer) to ensure the records are complete and are traceable to subjects within each clinical site. Data will be archived per the applicable policies and procedures as it relates to Data Extract process, Record Retention etc., and will be the source for data analysis. During data transfer, redundant copies will be stored at each critical stage of the transfer to safeguard adequate control over business continuity or disaster recovery of records. A copy of the electronic raw data will also be stored at each clinical site until receipt and storage by the sponsor has been confirmed.

The information collected during the procedure will include, but will not be limited to, the list below.

- RF application-mode per lesion (TGA-mode/Q-mode/other)
- Number of RF applications with QDot catheter (total/Q-mode/TGA-mode) and with non-study catheter
- Duration of RF applications with QDot catheter (total/Q-mode/TGA-mode) and with non-study catheter
- PVI ablation time (time between first RF application and last RF application on a PV before isolation confirmed and circumferential ablation achieved)
- Subject PVI ablation time (time between first RF application and last RF application before all PVI complete)
- Subject total ablation time (time between first RF application and last RF application in a subject)
- Ablation parameters per RF application: location, temperature, impedance, power, contact force, RF duration, ablation index, lesion information on CARTO®
- Ablation number on the generator for first RF application and last RF application per target (left PV targets, right PV targets and for targets outside the PV area)

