### 14.4. Primary and Secondary Endpoints, and Associated Hypotheses

#### 14.4.1. Primary Endpoints and Associated Hypotheses

The primary safety endpoint is acute safety defined as the Primary Adverse Events (PAEs) within the first 7 days. PAEs include the following AEs:

Atrio-Esophageal Fistula*	Phrenic Nerve Paralysis
Cardiac Tamponade/perforation	Pulmonary Vein Stenosis*
Death*	Stroke/CVA
Major Vascular Access Complication/Bleeding	Thromboembolism
Myocardial Infarction	TIA

\*Device or procedure related death, pulmonary vein stenosis and atrio-esophageal fistula that occur greater than one week (7 days) post-procedure are considered and analyzed as primary AEs.

The primary effectiveness endpoint is acute procedural success defined as achieving confirmation of entrance block in all targeted PVs after adenosine and/ or isoproterenol challenge. The use of non-study catheter for PVI will be considered as an effectiveness failure.

No formal statistical hypotheses will be formulated and performed for the primary endpoints.

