#### **14.8.4.3. Analyses of Secondary and Additional Endpoints**

No formal statistical hypotheses and inferential statistics will be formulated and performed for the secondary and additional endpoints. Details of analyses methods for secondary and additional endpoints will be provided in SAP.

Secondary Safety analysis for SADEs and AEs will be performed on the Safety Population. The neurological assessment related endpoints will be analyzed in the NAE population. Secondary Effectiveness (including Procedural Data) will be performed on the Effectiveness Population.

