10.4 Primary and Secondary Endpoint Analyses

Primary Safety

Primary safety outcome will be reported as primary adverse events (PAEs) (within 7 days of the intial mapping and ablation procedure, with exception for PV stenosis, death, tamponade and AEF). The number of events and the number and percentage of subjects experiencing primary adverse events will be reported. The primary safety endpoint will be summarized overall and by AE type, seriousness, severity, causality, anticipated or not. The Primary Safety analysis will be performed on the Safety Population.

Primary Effectiveness

Acute Procedural Success: Acute success is defined as achieving confirmation of entrance block in all targeted PVs after adenosine and/ or isoproterenol challenge. The number and percentage of subjects who have reached acute success will be summarized. Primary Effectiveness analysis will be performed on the Effectiveness Population.

Secondary Safety

The number of events and the number and percentage of subjects with SADEs, SAEs and non-SAEs during follow-up period (3 months) will be summarized overall and by AE type, seriousness, severity, causality, timing (< 7 days, 7-30 days, > 30 days), and outcome etc. The subjects with SADEs and SAEs will also be listed.

The number of events and the number and percentage of subjects with pre- and post-ablation asymptomatic and symptomatic cerebral emboli as determined by MRI evalutaions will be summarized. The incidence of new or worsening neurological deficits compared to baseline will be summarized and listed. NIHSS, mRS and MoCA scores at baseline and follow-up timepoints will be summarized and listed as well. The NAE endpoints will be analyzed in the NAE population.

Secondary Effectiveness

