The number of PV isolation achieved among all targeted veins and the number and percentage of subjects with PVI achieved with TGA mode only will be summarized and listed. The number of PV isolation achieved among all targeted veins and the number and percentage of subjects with PVI achieved with combined use of TGA and Q-mode will be summarized and listed. The number of PV with acute reconnection (touch-up) among all targeted veins and the number and percentage of subjects with touch-up ablations will be summarized and listed. Touch-up applications with TGA, Q-mode and non-study catheter will be summarized by PVs and subjects. PV ablations by a non-study catheter among all targeted veins and by subject will be summarized and listed. These analyses will be performed in the effectiveness population.

Additional Analyses on Procedural Data

Procedural data will be summarized and listed. For continuous variables, number of subjects with non-missing data, mean, standard deviation, median, 25% percentile, 75% percentile, minimum, and maximum will be reported. For categorical variables, the frequency and percentage will be presented for each category. Procedural data will be summarized in the effectiveness population.

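### An inserted subject who gets no TGA application and is isolated with a non-study catheter is a failure by definition, but enters neither effectiveness rate

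*SAP*

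**What the plan says.** The failure rule is in SAP 5.1: "The use of a non-study catheter for PVI will be considered an effectiveness failure". Protocol 14.4.1 agrees: "The use of non-study catheter for PVI will be considered as an effectiveness failure". The protocol synopsis carries the same rule. None of the three makes it depend on an earlier TGA application.

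The analysis set is defined in SAP 7 and in the same terms in Protocol 14.6. Membership needs insertion of the device and ablation with it in TGA mode for PVI, and the definition adds: "The subjects without any TGA mode application for PVI will be excluded from the effectiveness population".

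That set serves every effectiveness result. On the primary endpoint, SAP 10.4 says: "Primary Effectiveness analysis will be performed on the Effectiveness Population"; Protocol 14.8.4.2 says the same. On the secondary endpoint that describes catheter switches, SAP 10.4 says: "PV ablations by a non-study catheter among all targeted veins and by subject will be summarized and listed", and then, for that whole group of analyses: "These analyses will be performed in the effectiveness population". Protocol 14.8.4.3 concurs: "Secondary Effectiveness (including Procedural Data) will be performed on the Effectiveness Population".

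Three further places bear on the point:

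- Protocol 4.4 provides for Discontinued subjects, in whom the catheter is inserted but delivers no RF energy.
- Protocol 14.8.2 and SAP 10.2 tabulate and list disposition for everyone enrolled.
- Protocol 14.8.3 places procedural details, summarized and listed, in the Safety Population, which is every inserted subject.

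**The concern.** The endpoint definition and the analysis set do not fit together for one kind of subject. The definition calls a PVI completed with another catheter a failure in all circumstances. The set removes that subject if no TGA application came first. The secondary endpoint on non-study-catheter ablation would be the natural place to recover the event, but it uses the same set.

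The study is descriptive, so no error rate or power is at stake. What is at stake is the primary effectiveness estimate of a feasibility study whose stated purpose, in SAP 8, is to give preliminary estimates of safety and acute performance. For this group the omission can only raise the success rate and lower the reported rate of non-study-catheter use.

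**Working it through.** **Step 1. Sort the inserted subjects by what the two rules do to them.**

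| Inserted subject | Under SAP 5.1 | In Effectiveness Population (SAP 7) | Effect on reported success |
|---|---|---|---|
| TGA given, study catheter only, block confirmed | success | yes | counted as success |
| TGA given, then non-study catheter for PVI | failure | yes | counted as failure |
| No TGA, non-study catheter for PVI | failure | no | absent |
| No TGA, Q-mode only, block confirmed | success | no | absent |
| No PVI attempt | not reached by the non-study-catheter clause | no | absent |

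Only the third row is a defined failure that the set removes. The failure rule still has force through the second row.

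**Step 2. Inputs.** The plan states no expected success rate and no precision target, so there is no plan figure to reproduce. Protocol 14.7 and SAP 8 give about 50 subjects. Protocol 4.3.2 aims for 50 evaluable subjects, and Protocol 4.4 defines evaluable as catheter inserted, so 50 is the all-inserted denominator. Two quantities are assumptions:

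- k, the number of third-row subjects. The documents give no value and it may be 0.
- f, the number of failures inside the Effectiveness Population.

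The illustration also assumes that PVI was attempted in all 50 and that only third-row subjects are excluded.

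**Step 3. Formulas.** Successes s = 50 - k - f. Reported rate = s/(50 - k). Rate over all inserted = s/50. Difference = s/(50 - k) - s/50 = [s/(50 - k)] × (k/50). Intervals are Clopper-Pearson, two-sided 95%.

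**Step 4. Acute procedural success.**

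| k | f | Reported | All inserted | Difference |
|---|---|---|---|---|
| 0 | 0 | 50/50 = 100% (92.9-100) | 50/50 = 100% (92.9-100) | 0 |
| 1 | 0 | 49/49 = 100% (92.7-100) | 49/50 = 98.0% (89.4-99.9) | 2.0 points |
| 1 | 2 | 47/49 = 95.9% (86.0-99.5) | 47/50 = 94.0% (83.5-98.7) | 1.9 points |
| 2 | 0 | 48/48 = 100% (92.6-100) | 48/50 = 96.0% (86.3-99.5) | 4.0 points |
| 2 | 2 | 46/48 = 95.8% (85.7-99.5) | 46/50 = 92.0% (80.8-97.8) | 3.8 points |

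**Step 5. Secondary endpoint, by subject.** With k = 1 and no other use of a non-study catheter, the plan reports 0/49 = 0% (0-7.3). Over all inserted the result is 1/50 = 2.0% (0.1-10.6).

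**Step 6. The other direction.** Suppose the one excluded subject is instead a Q-mode-only success, with two failures counted. The reported rate is 47/49 = 95.92% and the all-inserted rate is 48/50 = 96.00%, a difference of -0.08 points.

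**The case against.** The strongest reply is that this is a chosen estimate and not a mistake. The objective in Protocol section 2 concerns the system used with the TGA algorithm, SAP 2 has every subject attempting TGA, and both documents define the same TGA-treated set in advance. An outcome rule does not by itself fix a denominator. This stands: the Effectiveness Population is a legitimate primary set, and the point is only that no rate beside it accounts for defined failures that fall outside it.

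A reader might go further and infer that the event is hidden or never counted. The documents do not support that. The subject is in the Safety Population and in the disposition output, and would be Discontinued if the study catheter delivered no energy. Protocol 14.8.3 plans a Safety Population listing of procedural details, and Protocol 8.2.3 collects this item: "Number of RF applications with QDot catheter (total/Q-mode/TGA-mode) and with non-study catheter". A device failure would also be documented and reported under Protocol 9.1.6 and 9.4.4. The SAP appendix says table and listing shells are provided separately, so silence in the SAP body does not show that a column is absent. What is established is narrower: the event is missing from the two effectiveness rates.

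One weakness in this reply remains. Protocol 14.8.3 puts procedural details in the Safety Population, while Protocol 14.8.4.3 and SAP 10.4 put procedural data in the Effectiveness Population, and SAP 10.3 does not repeat the Protocol 14.8.3 plan. Until these are reconciled, the listing cannot be relied on to show the switch. Disposition categories alone do not settle it either, because a subject with Q-mode but no TGA before the switch is not Discontinued.

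**Conclusion.** The point holds and is minor. Followed exactly, the plan can report 100% acute success when one inserted subject met its own failure definition. The size is about 2 points per such subject at 50, against an exact interval for 49/50 that runs from 89.4 to 99.9. It rests on at least one such subject occurring; if none does, nothing changes.

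Two stronger readings should not be drawn. First, a reader might take the 10% effectiveness attrition in SAP 8 (5 of 50) as a ceiling and quote 45/45 = 100% against 45/50 = 90.0%, a 10-point gap. The documents give no cause for that attrition, and nothing in them assigns it to this one path. Second, a reader might treat every exclusion from the Effectiveness Population as inflating the rate. A subject with no PVI attempt is not reached by the non-study-catheter clause, and a Q-mode-only subject with confirmed block is a success whose exclusion very slightly lowers the rate.

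**What to change.** Keep the Effectiveness Population analysis as primary and add the following to the SAP, with Protocol 14.6 and 14.8.4 aligned:

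1. A supplementary acute procedural success rate over all subjects with the study catheter inserted in whom PVI was attempted with any catheter. Non-study-catheter PVI counts as failure under SAP 5.1. Q-mode-only subjects with confirmed block count as successes and appear on a separate line.
2. PV ablation by a non-study catheter reported on the same denominator.
3. A listing of every inserted subject excluded from the Effectiveness Population, with the reason and the PVI outcome. Subjects with no PVI attempt are listed here and are not counted as failures.
4. One statement of which population carries procedural data, reconciling Protocol 14.8.3 with Protocol 14.8.4.3 and SAP 10.4.

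The cost is a few sentences, a few table columns and one listing. Protocol 8.2.3 already collects applications by mode and by non-study catheter, so no new data are needed. Classing a non-study-catheter PVI as failure applies the stated definition and is not imputation, so SAP 10.6 is not breached. The downside is that the supplementary rate may come out slightly lower than the primary one.

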**Table 3 Summary of Subject Assessments**

Assessments	Pre-ablation	Pre-discharge	7D (D6-8)	M1 (D23-37)	M3 (D76-104)	UNS
Clinic visit	●			● 9/10	●	●
Phone Call			● 			
Patient Informed Consent  /Demographics	●					
Medical/AF history	●					
Cardiac Medication and anti-coagulation Regimen	●	●	●	● 	●	●
CHA2DS2-Vasc Score	●					
NYHA functional Class Scale	●				●	
Pregnancy Test	● 					
Transthoracic Echo (TTE)	● 	●				
LA thrombus detection	● 					
ECG	● 	● 			● 	● 
Adverse events	●	●	●		●	●
AFL/AT/AF occurrence and repeat ablation		●	●		●	●
Endoscopy		● 				
Cerebral MRI	● 	● 		● 	● 	● 
Neurological Exam	● 	● 		● 	● 	● 
NIH Stroke Scale	● 	● 		● 	● 	● 
mRS	● 			● 	● 	● 
MoCA	● 			● 	● 	● 

1. May be substituted with a clinic visit.
2. To be completed within 60 days prior to ablation procedure
3. In all women of childbearing age and potential. To be completed within 1 week prior to ablation procedure.
4. To be performed within 30 days prior to procedure to determine the LA size and LVEF%, if the subject has undergone an imaging procedure within the last 6 months where the atrial size was assessed, the pre-procedure imaging assessment is not required.
5. To be completed the day before or the day of the study ablation procedure. Imaging modality TEE, ICE, CT or MRI.
6. To be collected if completed as standard of care.
7. To be completed within 72-hours pre-procedure.
8. To be completed within 72-hours post-procedure.
9. To be undertaken/collected if neurologic symptoms and/or new cerebral ischemic lesions identified/CVA/TIA reported in a prior evaluation.
10. To be completed only if a previous mandated test was missed, or if subject reports neurologic difficulties between scheduled follow-up visits and unscheduled assessment per investigator approval

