### **14.6. Analysis Sets**

The following analysis populations will be used to complete the analyses of data:

- **Safety Population:** The safety population will include all enrolled subjects who have the investigational device inserted, regardless if RF energy is delivered.
- **Effectiveness Population:** The effectiveness population will include all enrolled subjects who have had the investigational device inserted and underwent ablation with the study catheter used in conjunction with TGA mode for PVI. The subjects without any TGA mode application for PVI will be excluded from the effectiveness population.
- **Neurological Assessment Evaluable (NAE) Population:** The NAE Population will include all enrolled subjects who meet the eligibility criteria, have been treated with the study catheter and had any post-ablation neurological assessment. Assessment of incidence of new lesions or deficits requires availability of the associated pre-procedural assessment.

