10.1 General Conventions

All data will be summarized by descriptive analyses. No formal statistical inference will be made.

Standard descriptive summaries for continuous data include the number of observations with data, mean, standard deviation, median, minimum, and maximum values. For categorical data, the count and percent will be provided. Percentages will be based on the number of subjects without missing data.

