10.6 Handling of Missing Data

Missing questions will be queried for reasons and handled on an individual basis. No missing data imputation will be performed.

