Appendix: Tables, Listings and Graphs Shells

The tables, listings and graphs shells will be approved and provided separately.

End of Document

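### SAP 7 leaves open whether subjects with no pre-ablation MRI and a clean post-ablation MRI join the new-lesion denominator; if they do, unpaired subjects count only as non-events

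*SAP*

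**What the plan says.** SAP section 7 admits to the NAE population enrolled subjects who were treated with the study catheter and had at least one neurological assessment after ablation. It then gives a pairing rule: "Assessment of incidence of new lesions requires availability of pre-and post MRI". The next sentence reads: "The subjects without pre-MRI but no lesion on post-MRI will be included in the NAE population". Nothing is said about a subject with no pre-ablation MRI whose post-ablation MRI does show a lesion.

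Other places that bear on the point:

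- Protocol 14.6 has the pairing rule without the extra sentence: "Assessment of incidence of new lesions or deficits requires availability of the associated pre-procedural assessment".
- SAP 10.1: "Percentages will be based on the number of subjects without missing data".
- SAP 10.6: "Missing questions will be queried for reasons and handled on an individual basis". It also rules out imputation.
- SAP 10.4 plans, in the NAE population, the number and "percentage of subjects with pre- and post-ablation asymptomatic and symptomatic cerebral emboli as determined by MRI". It names no separate percentage for new lesions.
- SAP Appendix: "The tables, listings and graphs shells will be approved and provided separately".
- Protocol 8.2.1 makes the cerebral MRI mandatory within 72 hours before the procedure.

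**The concern.** If a post-ablation MRI counts as a neurological assessment, the subjects named in the added sentence are NAE members already. Read as a membership rule, the sentence then does nothing. Its position straight after the two-MRI rule suggests that it is meant as an exception to that rule. On that reading the decision to include an unpaired subject depends on the scan result: clean scans come in, and scans with a lesion, which may be new, stay out.

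Two analysts could therefore build different denominators from the same text, and one of the two versions selects on outcome. The measure is secondary and descriptive, so no test or decision rule is affected. It still merits a clear rule, ideally fixed before the scan results are known. Protocol 1.4.2 names cerebral embolism among four complications to be managed proactively, and Protocol 1.2.2 describes this as the first experience with the catheter and generator including TGA mode.

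**Working it through.** The plan states no new-lesion rate and no expected number of missing scans, so there is no figure to reproduce. The check has a textual part and an illustrative part.

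**Readings of the sentence**

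1. *Membership only, post-ablation MRI counts as an assessment.* The sentence is redundant. New-lesion incidence still needs both MRIs.
2. *Membership only, MRI alone does not count* (Protocol 8.2.1 and 8.2.4 list the MRI apart from the neurological exam). The sentence then admits clean-scan subjects with no other post-ablation assessment, and has no counterpart for subjects with a lesion. This case is probably rare.
3. *Exception to the two-MRI rule.* Clean unpaired subjects join the new-lesion denominator.

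No other text chooses between them. SAP 10.1 does not, because a clean unpaired scan can be taken as a known absence of new lesions or as a missing pair. SAP 10.4 refers only to the NAE population.

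**Direction under reading 3**

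Let N = subjects with a post-ablation MRI, m = those without a pre-ablation MRI, x = new lesions among the N − m paired subjects, and c = clean unpaired subjects.

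- Two-MRI rate: x / (N − m)
- Reading 3: x / (N − m + c)

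Since c ≥ 0, reading 3 can never exceed the two-MRI rate.

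**Expected size**

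Inputs: N = 50 (the planned sample size, all assumed scanned after ablation). The rest are assumptions: m = 1 or 2; p = true new-lesion rate; q = probability of any lesion, old or new, on the post-ablation scan of an unpaired subject (q ≥ p, taken here up to 0.40); missingness unrelated to lesion status. The two-MRI rate is then p in expectation, and reading 3 gives approximately

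(N − m)p / [(N − m) + m(1 − q)]

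| p | m | q | Reading 3 | Shift (points) |
|---|---|---|---|---|
| 10% | 1 | 0.40 | 4.9/49.6 = 9.88% | 0.12 |
| 10% | 2 | 0.10 | 4.8/49.8 = 9.64% | 0.36 |
| 20% | 1 | 0.40 | 9.8/49.6 = 19.76% | 0.24 |
| 20% | 2 | 0.20 | 9.6/49.6 = 19.35% | 0.65 |
| 30% | 1 | 0.40 | 14.7/49.6 = 29.64% | 0.36 |
| 30% | 2 | 0.30 | 14.4/49.4 = 29.15% | 0.85 |

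A higher q shrinks the shift further (p = 10%, m = 1, q = 0.80: 4.9/49.2 = 9.96%, shift 0.04). For scale, 10/50 has a Clopper-Pearson 95% interval of 10.0% to 33.7%. As a stress test with q = p = 20%, m = 5 gives 9/49 = 18.4% against 9/45 = 20.0%, and m = 10 gives 8/48 = 16.7% against 8/40 = 20.0%. Nothing in the documents suggests that so many required scans would be missed.

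**Example with m = 2**

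Ten new lesions in 48 paired subjects; one unpaired subject is clean and one has a lesion.

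- Two-MRI rate: 10/48 = 20.8%
- Reading 3: 10/49 = 20.4%
- True rate in the 50: 11/50 = 22.0% if the unpaired lesion is new, 10/50 = 20.0% if it is old

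**Against the true sample rate**

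Reading 3 can exceed the true rate, but only if an unpaired subject has an old lesion. Exact enumeration with p = 0.20 and q = 0.40 gives:

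| m | Below | Equal | Above | Expected reported rate |
|---|---|---|---|---|
| 1 | 20% | 60% | 20% | 19.8% |
| 2 | 36% | 36% | 28% | 19.5% |

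With no old lesions (q = p) it is never above.

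**The case against.** The literal text favours the harmless reading. The sentence speaks of belonging to the NAE population and mentions neither incidence nor a denominator, and the rule just before it demands both scans. Protocol 14.6 agrees, and SAP 10.1 together with the ban on imputation in SAP 10.6 leans the same way. The sentence may also have a genuine membership purpose if an MRI alone is not a neurological assessment. All of this stands as evidence for the paired denominator. None of it settles the matter, because no text says which sentence prevails and nothing explains why only clean scans are named.

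Second, a clean post-ablation scan does show that the subject has no new lesion on it, so including such subjects uses valid information. That is true of each subject. In aggregate it still selects on outcome, because the lesion-positive unpaired subjects are left out.

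Third, the practical effect is negligible. The pre-ablation scan is required and every input above is assumed. The only hint of missed tests in the schedule (Protocol Table 3, footnote 10: "To be completed only if a previous mandated test was missed") is attached to follow-up and unscheduled visits, and a missed pre-ablation scan cannot be made up after ablation. SAP 10.4 also allows all post-ablation lesions to be reported. This is accepted, and it is why the point is minor. That the table shells are kept separate is not a fault; it only means that they cannot resolve the question here.

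**Conclusion.** The point holds as a minor ambiguity. SAP 7 contains a sentence that includes unpaired subjects according to their scan result, and it does not say whether that sentence governs the new-lesion denominator. That it does is an inference from its placement, held with medium confidence. If it does, the bias relative to the two-MRI rate runs one way only. When pre-ablation scans are missing at random, the reported rate is also below the true rate in expectation, although in a single sample it may lie on either side. The shift is zero with no missing pre-ablation MRI and about 0.1 to 0.9 points with 1 or 2 missing out of 50, given assumed rates of 10% to 30% and q up to 0.40. This is well inside sampling error.

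**What to change.** Delete the sentence, or add that it concerns NAE membership and does not govern the new-lesion denominator. State that new-lesion incidence is computed in NAE subjects with both a pre- and a post-ablation MRI, following the pairing rule in Protocol 14.6, and show numerator and denominator. Say also which NAE definition applies, since Protocol 14.6 additionally requires subjects to meet the eligibility criteria and SAP 7 does not.

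Report subjects with a post-ablation MRI but no pre-ablation MRI as a separate count, split into lesion and no lesion. Optionally add one sensitivity row that includes all unpaired subjects and counts their lesions as new, labelled an upper bound because some may be old (11/50 = 22.0% in the example).

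The cost is one sentence and one count, with no change to data collection. The downside is that a few clean unpaired subjects, known to have no new lesion, leave the main denominator; they remain visible in the separate count.
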